### 4.2.2. Risks and expected adverse events

#### 4.2.2.1. Risk Determination

All screening procedures involve no more than minimal risk to participants. Similar procedures have been used for many years without severe adverse effects. These include blood sampling and ECG. Participants will be counselled about the following:

Blood draws: risks include discomfort as the needle goes through the skin and/or bruising. Infection, excess bleeding, clotting, or fainting are also possible, although unlikely.

ECG: risks include skin irritation due to ECG electrodes.

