## 4.2. Appendix 2: Adverse events

### 4.2.1. Definitions

**Adverse Event (AE):** any untoward medical occurrence in a patient or clinical study subject.

**Serious Adverse Event (SAE):** any untoward and unexpected medical occurrence or effect that:

- **Results in death**
- **Is life-threatening** – refers to an event in which the subject was at risk of death at the time of the event; it does not refer to an event which hypothetically might have caused death if it were more severe
- **Requires hospitalisation**
- **Results in persistent or significant disability or incapacity**
- **Is a congenital anomaly or birth defect**

Medical judgement should be exercised in deciding whether an AE is serious in other situations. Important AEs that are not immediately life-threatening or do not result in death or hospitalisation but may jeopardise the subject or may require intervention to prevent one of the other outcomes listed in the definition above, should also be considered serious.

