##### 5.3.2 Serious AEs

An SAE form should be completed and emailed to the Chief Investigator within 24 hours.

All SAEs should be reported to the Research Ethics Committee where in the opinion of the Chief Investigator, the event was:

- 'related', i.e. resulted from the administration of any of the research procedures; and
- 'unexpected', i.e. an event that is not listed in the protocol as an expected occurrence

Reports of related and unexpected SAEs should be submitted within 15 days of the Chief Investigator becoming aware of the event, using the NRES SAE form for non-IMP studies. The Chief Investigator must also notify the Sponsor of all SAEs.

Local investigators should report any SAEs as required by their Local Research Ethics Committee, Sponsor and/or Research & Development Office.

**Contact details for reporting SAEs**[[contact]](mailto:[contact])**CI email (and contact details below)****Email: [[contact]](mailto:[contact]) for the attention [name]****Please send SAE forms to: Department of Infectious Disease, Imperial College London, [name]****[contact] (Mon to Fri 09.00 – 17.00)**

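### Section 5.3.2 ties unexpectedness to listing alone, and the list in 4.2.2.1 has no seriousness limit, so on a literal reading a related serious infection or clot need not go to the REC

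*Protocol*

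**What the plan says.** Three parts of Appendix 2 of the protocol bear on this point.

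- **The REC rule (5.3.2, under 4.2.3).** "All SAEs should be reported to the Research Ethics Committee where in the opinion of the Chief Investigator, the event was" both related, meaning that it "resulted from the administration of any of the research procedures; and" unexpected, meaning "an event that is not listed in the protocol as an expected occurrence". Reports that meet both conditions are due within 15 days of the Chief Investigator becoming aware of the event. Separately, an SAE form goes to the Chief Investigator within 24 hours, the Sponsor is told of all SAEs, and local investigators report SAEs as their local ethics committee, the Sponsor or the R&D office requires.
- **The list (4.2.2.1).** It falls under the heading "Risks and expected adverse events" and is introduced by "Participants will be counselled about the following". For blood draws it gives discomfort and bruising, and then: "Infection, excess bleeding, clotting, or fainting are also possible, although unlikely". For the ECG it gives skin irritation. The same paragraph rates the risk of screening procedures as minimal at most and adds: "Similar procedures have been used for many years without severe adverse effects".
- **The SAE definition (4.2.1).** An SAE is "any untoward and unexpected medical occurrence or effect that" leads to one of the listed outcomes, hospital admission among them.

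**The concern.** Expectedness for reporting normally asks whether an event is foreseen in its nature and its severity. Here it depends only on whether the event's name appears in the protocol. Infection, bleeding, clotting and fainting are broad terms, and the first three run from trivial to dangerous. If a name on the list is enough, the grave form of an event inherits the expected status of its mild form.

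What is at stake is REC review of a serious harm that a research procedure caused in a healthy volunteer. In this rule the REC is the body outside the study team and the Sponsor. A serious event after procedures presented as minimal risk is one an ethics committee would want to see, because it calls that risk statement into question.

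**Working it through.** There is no figure to reproduce and no arithmetic to do. The check applies the stated rule to the stated list.

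**The rule.** A REC report is due if the event is (a) an SAE, (b) related to a research procedure, and (c) not listed in the protocol as expected. Condition (c) mentions neither severity nor outcome.

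**The list.** Section 4.2.2 is the only place in the document whose heading refers to expected events. Its qualifier for infection, excess bleeding, clotting and fainting concerns likelihood. The sentence on the absence of severe effects describes past experience. It is not attached to the listed terms as a limit.

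**Applying one to the other**, first taking (a) as settled by outcome alone:

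| Event caused by a screening blood draw | Serious by outcome | Related | Name on list | REC report due on literal reading |
|---|---|---|---|---|
| Bruise | No | Yes | Yes | No (not an SAE) |
| Unlisted complication with hospital admission | Yes | Yes | No | Yes, within 15 days |
| Infection or clot with hospital admission | Yes | Yes | Yes | No |

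The last two rows have the same seriousness and the same cause. They differ only in whether the event's name appears in 4.2.2.1.

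**Consistency with the protocol's own account.** If similar procedures have produced no severe effects over many years, a severe infection or clot is by that account not something to be expected. Section 5.3.2, applied as worded, classes it as expected all the same. The two passages need to be reconciled.

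**Interaction with 4.2.1.** The SAE definition also requires the event to be unexpected and does not say what that means there. If the 5.3.2 meaning is carried over, the listed infection or clot fails at step (a). It is then not an SAE, and the 24-hour form and the Sponsor notification would fall away as well.

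- Correcting 4.2.1 alone leaves the last row of the table as it is, because 5.3.2 and 4.2.2.1 are unchanged.
- Correcting 5.3.2 alone, for REC reporting only, may have no effect, because the event might be stopped at 4.2.1 before it reaches the REC test.

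Both places therefore have to change.

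**The case against.** The case on the other side has real substance.

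- **It is a counselling list.** The list is introduced as matter for counselling participants, and events called unlikely are not plainly listed as expected occurrences. This is fair, and it means that the list acts as the expected-event list by inference from its heading and from the lack of any other. But if it is not that list, the protocol has none and the REC test in 5.3.2 refers to nothing. The text needs repair on either reading.
- **The context implies mild forms.** The minimal-risk wording and the statement on severe effects suggest that only mild forms were meant. That is probably the intent, but the definition in 5.3.2 does not say so.
- **The Chief Investigator decides.** REC reporting turns on that person's opinion, and 4.2.2.1 gives grounds to judge a severe case unexpected. This stands. A severe case might well be reported, though someone who followed the definition literally could justify not reporting it.
- **Other routes exist.** The 24-hour form, Sponsor notification, local ethics committee requirements and the general instruction in 4.2.3 to report all adverse events remain. This also stands, and it confines the point to the protocol's own REC report, subject to the 4.2.1 problem.

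A reader might infer something stronger: that listed events are exempt from REC reporting at any severity, that the report is lost every time, or that these are the serious events most likely to occur. The documents do not support this. The Chief Investigator's judgement prevents any automatic exemption, and the protocol gives no event rates from which to rank the likely harms. Nor does the ECG entry add weight, since skin irritation has no plausible serious form.

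**Conclusion.** The point holds as a gap in wording, not as a certain loss of reporting. On its literal terms, 5.3.2 allows a related, serious form of infection, excess bleeding, clotting or fainting to be classed as expected and not sent to the REC, contrary to what 4.2.2.1 says about past experience of severe effects.

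The effect is limited to the protocol's REC report and its 15-day deadline. The events would be rare, and no frequency can be computed from the document. The conclusion rests on two assumptions: that 4.2.2.1 is the list to which 5.3.2 refers, and that the listing test is applied as written. If the 4.2.1 definition is also applied as written, the effect could extend to the Chief Investigator and Sponsor routes, which is why the sections should be corrected together. The change is worth making because the safety-oversight gap is avoidable and the remedy is small.

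**What to change.** 1. In 5.3.2, add a sentence stating that the events listed in 4.2.2.1 count as expected only in their non-serious form, so that a serious form of a listed event is unexpected for REC reporting. The two-part test of related and unexpected stays in place.
2. In 4.2.1, delete the condition that an SAE be unexpected, so that seriousness depends on outcome and expectedness is judged only in 5.3.2. Without this, a listed event may never reach the REC test.

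The cost is about a sentence of new wording, one short deletion, and at most a rare additional REC report. No assessment, visit or data item changes.

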#### 4.2.3. Reporting procedures

All adverse events should be reported. Depending on the nature of the event the reporting procedures below should be followed. Any questions concerning adverse event reporting should be directed to the Chief Investigator in the first instance.

##### 5.3.1 Non serious AEs

All such events, whether expected or not, should be recorded - it should be specified if only some non-serious AEs will be recorded. Any reporting should be consistent with the purpose of the trial end points.

##### 5.3.2 Serious AEs

An SAE form should be completed and emailed to the Chief Investigator within 24 hours.

All SAEs should be reported to the Research Ethics Committee where in the opinion of the Chief Investigator, the event was:

- 'related', i.e. resulted from the administration of any of the research procedures; and
- 'unexpected', i.e. an event that is not listed in the protocol as an expected occurrence

Reports of related and unexpected SAEs should be submitted within 15 days of the Chief Investigator becoming aware of the event, using the NRES SAE form for non-IMP studies. The Chief Investigator must also notify the Sponsor of all SAEs.

Local investigators should report any SAEs as required by their Local Research Ethics Committee, Sponsor and/or Research & Development Office.

**Contact details for reporting SAEs**[[contact]](mailto:[contact])**CI email (and contact details below)****Email: [[contact]](mailto:[contact]) for the attention [name]****Please send SAE forms to: Department of Infectious Disease, Imperial College London, [name]****[contact] (Mon to Fri 09.00 – 17.00)**

### 4.3. Appendix 3: Abbreviations

Abbreviation	Term
ADA	Anti-Drug Antibody
AE	Adverse Event
ALP	Alkaline Phosphatase
ALRI	Acute Lower Respiratory Infection
ALT	Alanine Aminotransferase
AP	Analytical Plan
APTT	Activated Partial Thromboplastin Time
AR	Adverse Reaction
AST	Aspartate Aminotransferase
AST	Aspartate Transaminase
ATS	American Thoracic Society
AUC	Area Under the Curve
BD	Twice Daily
BMI	Body Mass Index
cGMP	Current Good Manufacturing Practices
CK	Creatine Kinase
CONSORT	Consolidated Standards of Reporting Trials
COPD	Chronic Obstructive Pulmonary Disease
CRF	Case Report Form
CRP	C-reactive Protein
CYP450	Cytochrome 450
DNA	Deoxyribonucleic acid
DMID	Division of Microbiology and Infectious Disease
ECG	Electrocardiogram
ECSC	European Coal and Steel Community
ELISA	Enzyme-linked Immunosorbent Assay
EMA	European Medicines Agency
ERS	European Respiratory Society

EU	European Union
FEV	Forced Expiratory Volume
FOT	Forced oscillation technique
FSH	Follicle Stimulating Hormone
FVC	Forced Vital Capacity
GAD	Generalised Anxiety Disorder
GCP	Good Clinical Practice
GDPR	General Data Protection Regulation
GP	General Practitioner
HAV	Hepatitis A
HbA1c	Haemoglobin A1c
HBV	Hepatitis B
HCV	Hepatitis C
HIV	Human Immunodeficiency Virus
HVC	Human Viral Challenge
ICF	Inform Consent Form
ICH	International Council for Harmonisation
ICMJE	International Committee of Medical Journal Editors
IgA	Immunoglobulin A
IgG	Immunoglobulin G
IM	Intramuscular
IMP	Investigational Medicinal Product
IUD	Intrauterine Device
IV	Intravenous
LMIC	Low to Medium Income Country
LRT	Lower Respiratory Tract
MCH	Mean Corpuscular Haemoglobin
MCHC	Mean Corpuscular Haemoglobin Concentration
MCID	Minimal Clinically Important Difference
MCV	Mean Corpuscular Volume
MHRA	Medicines and Healthcare products Regulatory Agency
MOI	Monoamine Oxidase Inhibitors
NIMP	Non-Investigational Medicinal Product
NPS	Nasopharyngeal Swab
PBMC	Peripheral Blood Mononuclear Cell
PCA	Principal Component Analysis
PCR	Polymerase Chain Reaction
PEF	Peak expiratory flow
PFM	Peak flow meter
PFU	Plaque Forming Unit
PHQ	Patient Health Questionnaire
PI	Principal Investigator
PK	Pharmacokinetic
PT	Prothrombin Time
qRT-PCR	Quantitative Reverse Transcriptase-Polymerase Chain Reaction
RBC	Red Blood Cell
REC	Research Ethics Committee

RNA	Ribonucleic acid
RSI	Reference Safety Information
RSV	Respiratory Syncytial Virus
SAE	Serious Adverse Event
SME	Sponsor's Medical Expert
SmPC	Summary of Product Characteristics
SoA	Schedule of Activities
SOP	Standard Operating Procedure
SUSAR	Suspected Unexpected Adverse Reaction
T	Troponin
TDS	Three Times Daily
TMF	Trial Master File
TSH	Thyroid Stimulating Hormone
TSH	Thyroid Stimulating Hormone
TSS	Total Symptoms Score
UK	United Kingdom
URT	Upper Respiratory Tract
WBC	White Blood Cell
β-HCG	β-human chorionic gonadotrophin

#### 4.4. Appendix 4: Toxicity Grading Scale for Laboratory AEs

Toxicity Grading Scale for Lab AEs			Lab Range	Grade 1	Grade 2	Grade 3	Grade 4
Sodium	Elevated	mmol/L	145	146-147	148-149	150-155	>155
Sodium	Low	mmol/L	135	132-134	130-131	125-129	<125
Potassium	Elevated	mmol/L	5.1	5.2-5.3	5.4-5.5	5.6-6.5	>6.5
Potassium	Low	mmol/L	3.5	3.2-3.3	3.0-3.1	2.5-2.9	<2.5
Urea	Elevated	mmol/L	1.7-8.3	8.4-9.3	9.4-11.0	>11.0	Requires Dialysis
Creatinine (Female)	Elevated	µmol/L	49-92	101-138	139-276	>277	Requires Dialysis
Creatinine (Male)	Elevated	µmol/L	66-112	123-168	169-336	>336	Requires Dialysis

Bilirubin	Normal LFTs	µmol/L	0-20	22-30	31-40	41-60	>60
Bilirubin	Abnormal LFTs	µmol/L	0-20	22-25	26-30	31-35	>35
ALP (Female)	Elevated	IU/L	104	114-208	209-312	313-1040	>1040
ALP (Male)	Elevated	IU/L	129	142-258	259-387	388-1290	>1290
ALT (Female)	Elevated	IU/L	35	39-88	89-175	176-350	>350
ALT (Male)	Elevated	IU/L	50	55-125	126-250	251-500	>500
AST (Female)	Elevated	IU/L	31	34-78	79-155	156-310	>310
AST (Male)	Elevated	IU/L	37	41-93	94-185	186-370	>370
Albumin	Low	g/L	34-50	28-31	25-27	<25	-
